7.2. Run-in Treatment(s)

There will be a run-in period for:

- Patients who are not receiving the maximal dose of a PCSK9 inhibitor antibody or whose dose has not been stable for at least 8 weeks before the screening visit
- Patients whose maximally tolerated statin has not been stable for at least 4 weeks before the screening visit
- Patients whose background LMT (other than statin or PCSK9 inhibitor antibody) has not been stable for at least 4 weeks (6 weeks for fibrates) before the screening visit

During this run-in period, patients will be stabilized on their statin, PCSK9 inhibitor antibody, and other background LMT (as applicable), and patients receiving alirocumab 75 mg SC Q2W will have their dose up-titrated to 150 mg SC Q2W or 300 mg SC Q4W. The duration of the run-in period will depend on the time needed for the patient to stabilize on their background LMT.

Patients have to be consented prior to entering the run-in period.

7.3. Background Treatment(s)

All patients should be on a stable, maximally-tolerated LMT regimen throughout the duration of the study.

All patients should be on maximal background LMT, which includes a stable maximally tolerated statin and stable PCSK9 inhibitor antibody. Patients with HeFH who are not on a statin are allowed to participate if there is documentation of inability to tolerate at least 2 statins due to muscle symptoms. Inability to tolerate a statin should be due to skeletal muscle-related symptoms, other than those due to strain or trauma, such as pain, aches, weakness, or cramping, that began or increased during statin therapy and stopped when statin therapy was discontinued.

For the background LMT, sites must follow the national product label for patient safety monitoring and management. The dose of statin and of PCSK9 inhibitor, such as alirocumab or evolocumab, as well as other LMT (if applicable), should remain stable throughout the study duration, from screening through the EOS visit. If a patient is not considered to be on a maximum tolerated LMT regimen (high-intensity statin, PCSK9 inhibitor antibody, ezetimibe, etc) at the start of the run-in or at screening, reasons why or why not (eg, due to intolerance, lack of efficacy, not marketed in the region) the patient is taking/not taking the various treatments will need to be documented in the CRF.

7.4. Dose Modification and Study Treatment Discontinuation Rules

7.4.1. Dose Modification

Dose modification for an individual patient is not allowed.

7.4.2. Study Drug Discontinuation

Study treatment should be continued whenever possible. In the event study drug dosing is stopped, it should be determined if the stop can be made temporarily; permanent discontinuation should be a last resort. Regardless, the patient should remain in the study treatment period as long as possible.

Patients who prematurely discontinue study drug should remain in the study and undergo all study visits and procedures, with the exception of dosing with study drug. At the time of study drug

discontinuation, the patient should have, as soon as possible, an unscheduled visit with assessments normally planned at EOT visit (this should take place within 5 days of discontinuation of study drug, if possible), and then resume the original study schedule until the EOS visit. In case of early discontinuation before week 16, all efforts should be made to perform EOT assessments as soon as possible.

Patients who permanently discontinue from study drug, and who opt to withdraw from the study, will be asked to complete study assessments, per Section 6.3.

7.4.2.1. Reasons for Permanent Discontinuation of Study Drug

Study drug dosing will be permanently stopped in a patient in the event of the following, but not limited to:

- Evidence of pregnancy
- Acute systemic injection/infusion reactions with AEs including, but not limited to, anaphylaxis, laryngeal/pharyngeal edema, severe bronchospasm, chest pain, seizure, or severe hypotension
- Patient requires a prohibited concomitant medication during the study. The principal investigator should contact the Regeneron study monitor. Based on the discussion, study drug may be continued, or may be temporarily or permanently discontinued
- Patient withdraws consent

The investigator may permanently discontinue dosing with study drug at any time, even without consultation with the medical monitor, if the urgency of the situation requires immediate action and if this is determined to be in the patient's best interest. However, the medical monitor should be contacted as soon as possible in any case of permanent study drug discontinuation.

7.5. Management of Acute Reactions

7.5.1. Acute Infusion Reactions

Emergency equipment and medication for the treatment of infusion reactions must be available for immediate use. All infusion reactions must be reported as AEs (as defined in Section 9.4.1) and graded using the grading scales, as instructed in Section 9.5.1.

7.5.1.1. Interruption of the Infusion

The infusion should be interrupted if any of the following AEs are observed:

- cough
- rigors/chills
- rash, pruritus (itching)
- urticaria (hives, welts, wheals)
- diaphoresis (sweating)
- hypotension

- dyspnea (shortness of breath)
- vomiting
- flushing

The reaction(s) should be treated symptomatically, and the infusion may be restarted at 50% of the original rate.

If investigators feel there is a medical need for treatment of the reaction or need for discontinuation of the infusion, other than described above, they should use clinical judgment to provide the appropriate response according to typical clinical practice.

7.5.1.2. Termination of the Infusion

The infusion should be terminated and NOT restarted if any of the following AEs occur:

- anaphylaxis*
- severe bronchospasm
- chest pain
- seizure
- severe hypotension
- other neurological symptoms (confusion, loss of consciousness, paresthesia, paralysis, etc.)
- any other symptom or sign that, in the opinion of the investigator, warrants discontinuation of the infusion

*Consider anaphylaxis if the following is observed ([Sampson 2006](#)): acute onset of an illness (minutes to several hours) with involvement of the skin, mucosal tissue, or both (eg, generalized hives, pruritus or flushing, swollen lips-tongue-uvula) AND AT LEAST ONE OF THE FOLLOWING:

- a. Respiratory compromise (eg, dyspnea, wheeze-bronchospasm, stridor, reduced peak expiratory flow, hypoxemia)
- b. Reduced BP or associated symptoms of end-organ dysfunction (eg, hypotonia [collapse], syncope, incontinence)

7.5.2. Acute Injection Reactions

7.5.2.1. Systemic Injection Reactions

Acute systemic reactions following administration of study drug (IV or SC), should be treated using clinical judgment, based on standard clinical practice, in order to determine the appropriate response.

7.5.2.2. Local Injection Site Reactions

Local injection site reactions must be reported as AEs and graded according to the Food and Drug Administration (FDA) September 2007 Guidance for Industry, Toxicity Grading Scale for Healthy

Adult and Adolescent Volunteers Enrolled in Preventive Vaccine Clinical Trials (provided in the study Regulatory Binder, also see Section 9.5.1).

7.6. Method of Treatment Assignment

Patients will be randomized within either Group A (SC treatment regimens) in a 1:1:1:1 ratio or Group B (IV treatment regimens) in a 1:1:1 ratio. Enrollment of IV cohorts will occur before enrollment of SC cohorts; accordingly, enrollment of Group A will not begin until Group B enrollment is completed. There will be 144 patients randomized to Group A (36 patients per treatment group), with 108 patients exposed to SC evinacumab and 36 exposed to SC placebo. There will be 108 patients randomized to Group B (36 patients per treatment group), with 72 patients exposed to IV evinacumab and 36 exposed to IV placebo.

Patients in Group A will receive treatment from day 1 through week 16 (last dose of study drug at week 15). Patients in Group B will receive treatment from day 1 through week 24 (last dose of study drug week 20). Patients will be randomized to a treatment group according to a central randomization scheme provided by an interactive voice response system (IVRS)/interactive web response system (IWRS) to the designated study pharmacist (or qualified designee).

Randomization will be stratified by study treatment route of administration (Group A or B), high-intensity statin (Yes/No), and HeFH (Yes/No) at baseline. High-intensity statin is defined as rosuvastatin 20 mg or 40 mg daily, atorvastatin 40 mg or 80 mg daily, or simvastatin 80 mg daily (if already on this dose for >1 year). To ensure that an adequate number of patients with HeFH are included, randomization will be stratified 2:1 (HeFH:non-HeFH; 24:12) within each treatment group.

7.6.1. Blinding

Study patients, principal investigators, and study site personnel will remain blinded to all randomized study treatment group assignments throughout the study. The Regeneron Study Director, Medical Monitor, Study Monitor, and any other Regeneron and contract research organization (CRO) personnel who are in regular contact with the study site will remain blinded to all patient randomization assignments. All lipid results will be blinded from after randomization until the week 36 visit for the IV cohorts, and until database lock for the SC cohorts.

Due to differences in the color of the study drug as compared to placebo, an unblinded pharmacist or qualified unblinded designee will prepare the IV infusion bags and SC injections. Further details are provided in the pharmacy manual.

7.6.2. Emergency Unblinding

Unblinding of treatment assignment for a patient may be necessary due to a medical emergency or any other significant medical event (eg, pregnancy).

If unblinding is required:

- Only the investigator will make the decision to unblind the treatment assignment
- Only the affected patient will be unblinded

- The designated study pharmacist(s)/designee at the study site will provide the treatment assignment to the investigator. If there is no study pharmacist, the investigator for the site will unblind the patient
- The investigator will notify Regeneron and/or designee before unblinding the patient, whenever possible

Treatment assignment is not to be provided to site personnel, other than the unblinded study pharmacist (when applicable), at any time during the conduct of the study, except in the case of a true emergency. In the event that there is no study pharmacist, the individual at the site fulfilling that role will be the only unblinded member of the site personnel.

7.7. Treatment Logistics and Accountability

7.7.1. Packaging, Labeling, and Storage

A medication numbering system will be used to label blinded investigational study drug. Lists linking medication numbers with product lot numbers will be maintained by the groups (or companies) responsible for study drug packaging. In order to maintain the blind, these lists will not be accessible to individuals involved in study conduct.

Study drug will be stored at the site at a temperature of 2°C to 8°C; storage instructions will be provided in the pharmacy manual.

7.7.2. Supply and Disposition of Treatments

Study drug will be shipped at a temperature of 2°C to 8°C to the investigator or designee at regular intervals or as needed during the study. At specified time points during the study (eg, interim site monitoring visits), at the site close-out visit, and following drug reconciliation and documentation by the site monitor, all opened and unopened study drug will be destroyed, or returned to the sponsor or designee.

7.7.3. Treatment Accountability

All drug accountability records must be kept current.

The investigator must be able to account for all opened and unopened study drug. These records should contain the dates, quantity, and study medication

- dispensed to each patient
- returned from each patient (if applicable), and
- disposed of at the site or returned to the sponsor or designee

All accountability records must be made available for inspection by the sponsor and regulatory agency inspectors; photocopies must be provided to the sponsor at the conclusion of the study.

7.7.4. Treatment Compliance

All drug compliance records must be kept current and made available for inspection by the sponsor and regulatory agency inspectors.

7.8. Concomitant Medications and Procedures

Any treatment administered from the time of informed consent to the final study visit will be considered concomitant medication. This includes medications that were started before the study and are ongoing during the study.

7.8.1. Prohibited Medications and Procedures

Any background medical LMT, which has not been stable for at least 4 weeks prior to the screening visit, is prohibited.

- Simvastatin 80 mg (unless having received for > 1 years), lomitapide, and mipomersen are prohibited.
- LDL apheresis is a prohibited procedure.

7.8.2. Permitted Medications and Procedures

The use of all medications and nutritional supplements known to alter serum lipids, including (but not limited to) statins, ezetimibe, fibrates, niacin, bile acid resins, red yeast rice, and PCSK9 inhibitor antibodies is permitted, as long as that therapy has been stable for at least 4 weeks (6 weeks for fibrates and 8 weeks for PCSK9 inhibitor antibodies) prior to the screening visit. Patients should continue taking their background medical LMT for the duration of the study, starting at screening and continuing through the EOS visit.

Thyroid replacement therapy can be used, if the dosage of thyroxine has been stable for at least 12 weeks prior to the screening visit (week -2).

8. STUDY SCHEDULE OF EVENTS AND PROCEDURES

8.1. Schedule of Events

Study assessments and procedures are presented by study period and visit in [Table 1](#), [Table 2](#), [Table 3](#), [Table 4](#), [Table 5](#), [Table 6](#), and [Table 7](#).

Table 1: Screening Schedule of Events – Patients Requiring Medication Change or Daily Statin Stabilization at Study Entry

Visit Number	Visit 1a Pre-Screening	Visit 1 Full Screening Visit
Visit Window (Day)		Day -14 to -1
Week		-2
Screening/Baseline:		
Informed Consent	X	
██████████ ██████████		X
Medication Adjustment	X	
Inclusion/Exclusion	X	X
Medical History/Surgical History, Alcohol Habits, Smoking Habits		X
Demographics		X
Treatment:		
Concomitant Medications	X	X
Query LMT compliance	X	X
Safety:		
Height		X
Weight		X
Vital Signs		X
Physical Examination		X
Electrocardiogram ³		X
Contraception Use Reminder ¹	X	X
Remind male patients to use condoms	X	X
Adverse Events	X	X
Laboratory Testing²:		
Hematology		X
Chemistry		X
Urinalysis		X
Core Lipid Panel (8-hour fasting sample)	X	X
HbA1c	X	X
Pregnancy Test	Urine	Serum
Hepatitis B and C serology		X
TSH		X
FSH		X
PK and Ab Samples:		
Research Samples (biomarkers)		X
Other:		
Review of diet	X	X

Table 2: Screening Schedule of Events – Patients on Stable Statin, PCSK9 Inhibitor Antibody and Lipid Modifying Therapy Regimen at Study Entry

Visit Number	Visit 1 Screening Visit
	Day-14 to -1
Screening/Baseline:	
Informed Consent	X
██████████ ██████████	X
Inclusion/Exclusion	X
Medical/Surgical History, Alcohol habits, Smoking habits	X
Demographics	X
Treatment:	
Concomitant Medications	X
Query LMT compliance	X
Safety:	
Height	X
Weight	X
Vital Signs	X
Physical Examination	X
Electrocardiogram ³	X
Contraception Use Reminder ¹	X
Remind male patients to use condoms	X
Adverse Events	X
Laboratory Testing²:	
Hematology	X
Chemistry	X
Urinalysis	X
Core Lipid Panel (8-hour fasting sample)	X
HbA1c	X
Pregnancy Test	Serum
Hepatitis B and C serology	X
TSH	X
FSH	X
PK and Ab Samples:	
Research samples (biomarkers)	X
Other:	
Review of diet	X

Table 3: Schedule of Events for SC Treatment Group A

	Double-Blind Treatment Period																
	Visit 2	Visit 3	Visit 4	Visit 5	Visit 6	Visit 7	Visit 8	Visit 9	Visit 10	Visit 11	Visit 12	Visit 13	Visit 14	Visit 15	Visit 16	Visit 17	Visit 18/ EOT
Day	1	8	15	22	29	36	43	50	57	64	71	78	85	92	99	106	113
Visit Window (Day)	±3	±3	±3	±3	±3	±3	±3	±3	±3	±3	±3	±3	±3	±3	±3	±3	±3
Week	0	1	2	3	4	5	6	7	8	9	10	11	12	13	14	15	16
Screening/Baseline:																	
Randomization	X																
Treatment:																	
Administer SC Study Drug ^{4, 7, 8}	X	X	X	X	X	X	X	X	X	X	X	X	X	X	X	X	
Concomitant Medications	X	X	X	X	X	X	X	X	X	X	X	X	X	X	X	X	X
Query LMT compliance	X	X	X	X	X	X	X	X	X	X	X	X	X	X	X	X	X
Safety:																	
Weight	X								X								X
Vital Signs ¹¹	X	X	X	X	X	X	X	X	X	X	X	X	X	X	X	X	X
Physical Examination																	X
Electrocardiogram ³																	X
Contraception Use Reminder ¹	X	X	X	X	X	X	X	X	X	X	X	X	X	X	X	X	X
Remind male patients to use condoms	X	X	X	X	X	X	X	X	X	X	X	X	X	X	X	X	X
Adverse Events	X	X	X	X	X	X	X	X	X	X	X	X	X	X	X	X	X
Laboratory Testing²:																	
Hematology	X		X		X				X				X				X
Chemistry	X		X		X				X				X				X
Urinalysis	X		X		X				X				X				X
Core Lipid Panel	X		X		X		X		X		X		X		X		X

	Double-Blind Treatment Period																
	Visit 2	Visit 3	Visit 4	Visit 5	Visit 6	Visit 7	Visit 8	Visit 9	Visit 10	Visit 11	Visit 12	Visit 13	Visit 14	Visit 15	Visit 16	Visit 17	Visit 18/ EOT
Day	1	8	15	22	29	36	43	50	57	64	71	78	85	92	99	106	113
Visit Window (Day)	±3	±3	±3	±3	±3	±3	±3	±3	±3	±3	±3	±3	±3	±3	±3	±3	±3
Week	0	1	2	3	4	5	6	7	8	9	10	11	12	13	14	15	16
Specialty Lipid Panel	X				X				X				X				X
HbA1c																	X
hs-CRP	X								X								X
Pregnancy Test	U				U				U				U				U
PK and Research Samples:																	
PK (evinacumab, alirocumab) ⁴ , ANGPTL3, PCSK9 sample	X	X	X		X				X		X		X				X
Anti-evinacumab antibody sample	X				X												X
Research samples (biomarkers)	X						X						X				X
LDL-R function sample ⁵	X																
[REDACTED]	X		X														
[REDACTED]	X																
Other:																	
Review of low fat diet	X	X	X	X	X	X	X	X	X	X	X	X	X	X	X	X	X

Table 4: Schedule of Events for IV Treatment Group B

	Double Blind Treatment Period									Open-Label Treatment Period					
	Visit 2	Visit 3	Visit 4	Visit 5	Visit 6	Visit 7	Visit 8	Visit 9	End of DBTP Visit 10	Visit 11	Visit 12	Visit 13	Visit 14	Visit 15	Visit 16
Day	1	15	29	43	57	85	113	141	169	197	225	253	281	309	337
Visit Window (Day)	±3	±3	±3	±3	±3	±3	±3	±3	±3	±3	±3	±3	±3	±3	±3
Week	0	2	4	6	8	12	16	20	24	28	32	36	40	44	48
Screening/Baseline:															
Randomization	X														
Treatment:															
Administer Double-Blind IV Study Drug ^{4,7}	X		X		X	X	X	X							
Administer Open-Label IV Study Drug ^{4,7}									X#	X	X	X	X	X	X
Concomitant Medications	X	X	X	X	X	X	X	X	X	X	X	X	X	X	X
Query LMT compliance	X	X	X	X	X	X	X	X	X	X	X	X	X	X	X
Safety:															
Weight	X	X	X	X	X	X	X	X	X	X	X	X	X	X	X
Vital Signs ¹¹	X	X	X	X	X	X	X	X	X	X	X	X	X	X	X
Physical Examination									X						
Electrocardiogram ³									X						X
Contraception Use Reminder ¹	X	X	X	X	X	X	X	X	X	X	X	X	X	X	X
Remind male patients to use condoms	X	X	X	X	x	x	X	x	X	X	X	X	X	X	X
Adverse Events	X	X	X	X	X	X	X	X	X	X	X	X	X	X	X
Laboratory Testing²:															
Hematology	X	X	X		X	X	X	X	X	X	X	X	X	X	X
Chemistry	X	X	X		X	X	X	X	X	X	X	X	X	X	X
Urinalysis	X	X	X		X	X	X	X	X	X	X	X	X	X	X
Core Lipid Panel	X	X	X	X	X	X	X	X	X	X	X	X	X	X	X
Specialty Lipid Panel	X		X		X	X	X	X	X	X	X	X	X	X	X
HbA1c						X			X			X			X
hs-CRP	X					X			X			X			X
Pregnancy Test	U		U		U	U	U	U	U	U	U	U	U	U	U

	Double Blind Treatment Period									Open-Label Treatment Period					
	Visit 2	Visit 3	Visit 4	Visit 5	Visit 6	Visit 7	Visit 8	Visit 9	End of DBTP Visit 10	Visit 11	Visit 12	Visit 13	Visit 14	Visit 15	Visit 16
Day	1	15	29	43	57	85	113	141	169	197	225	253	281	309	337
Visit Window (Day)	±3	±3	±3	±3	±3	±3	±3	±3	±3	±3	±3	±3	±3	±3	±3
Week	0	2	4	6	8	12	16	20	24	28	32	36	40	44	48
PK and Research Samples:															
PK (evinacumab, alirocumab) ⁴ , ANGPTL3, and PCSK9	X	X	X	X	X		X		X			X			X
Anti-evinacumab antibody sample	X		X			X			X			X			X
Research samples (biomarkers)	X			X		X			X			X			X
LDL-R function sample ⁵	X														
████████████████████	X	X													
████████████████████	X														
Other:															
Review of low fat diet	X	X	X	X	X	X	X	X	X	X	X	X	X	X	X

Table 5: Schedule of Events for IV Treatment Group B (Continued for Open-Label)

	Open-Label Treatment Period - Continued (Group B)					
	Visit 17	Visit 18	Visit 19	Visit 20	Visit 21	End of Open-Label Visit 22
Day	365	398	421	449	477	505
Visit Window (Day)	±3	±3	±3	±3	±3	±3
Week	52	56	60	64	68	72
Treatment:						
Administer Open-Label IV Study Drug ^{4,7}	X	X	X	X	X	
Concomitant Medications	X	X	X	X	X	X
Query LMT compliance	X	X	X	X	X	X
Safety:						
Weight	X	X	X	X	X	X
Vital Signs ¹¹	X	X	X	X	X	X
Contraception Use Reminder ¹	X	X	X	X	X	X
Remind male patients to use condoms	X	X	X	X	X	X
Adverse Events	X	X	X	X	X	X
Laboratory Testing²:						
Hematology			X			X
Chemistry			X			X
Urinalysis			X			X
Core Lipid Panel	X	X	X	X	X	X
Specialty Lipid Panel			X			X
HbA1c			X			X
hs-CRP			X			X
Pregnancy Test	U	U	U	U	U	U
PK and Research Samples:						
PK (evinacumab, alirocumab) ⁴ , ANGPTL3, and PCSK9			X			X
Anti-evinacumab antibody sample			X			X
Research samples (biomarkers)			X			X
Other:						

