Five (5) mg/kg IV Q4W is selected as the alternative lower dose as it is expected to differentiate from 15 mg/kg in evinacumab exposure, ANGPTL3 binding, TG reduction and possibly, LDL-C reduction in patients with HeFH. In otherwise healthy subjects with elevated TGs and LDL-C in study R1500-HV-1214, single-dose administrations of evinacumab 75, 150, and 250 mg SC and 5, 10, and 20 mg/kg IV led to dose-dependent target engagement and reductions in LDL-C and TGs. The total exposure (AUC) of evinacumab after 5 mg/kg IV is 4- to 5-fold lower than the predicted area under curve for 15 mg/kg IV, due to non-linearity in PK. In addition, the serum concentration of evinacumab in the single-dose study (R1500-HV-1214) after 5 mg/kg IV was above 100 mg/L for 2-3 days. Inclusion of this dose will inform whether ANGPTL3 saturation is

needed for maximal LDL-C reduction in patients with HeFH. On the other hand, 5 mg/kg IV Q4W is expected to provide some benefit in decreasing LDL-C in patients with HeFH, as evinacumab concentration after 5 mg/kg IV was much greater than that after the 250 mg SC dose, which has shown to reduce LDL-C to a varying degree in patients with HoFH (study R1500-CL-1331). Low-density lipoprotein response, although observed to lag behind drug exposure, is expected to be stabilized following 8 weeks of treatment with a Q4W dosing interval.

For the open-label phase, 15 mg/kg IV Q4W will be administered. Target saturation is expected during the 4-week dosing interval and patients are most likely to have a sustained, maximal LDL-C reduction compared to lower doses. In addition, safety information can be collected at the highest dose of evinacumab and provide the most relevant information to characterize the benefit-risk profile of evinacumab over long-term use.

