Randomization will be stratified by high-intensity statin (Yes/No) and HeFH (Yes/No) at baseline. High-intensity statin is defined as rosuvastatin 20 mg or 40 mg daily, atorvastatin 40 mg or 80 mg daily, or simvastatin 80 mg daily (if already on this dose for >1 year). To ensure an adequate number of patients with HeFH are included in this study and exposed to each dose, randomization will be stratified 2:1 (HeFH:non-HeFH; 24:12) within each treatment group.

Investigational medicinal product (IMP) administration during the double-blind treatment period will take place at the site and possibly, by visiting home nurses (only for the SC group). The IMP will be administered at the site on the day of randomization, after all samples for clinical laboratory evaluation have been obtained. In order to ease burden for those patients randomized to receive SC IMP, visiting home nurses may be utilized to administer SC IMP on odd visit dates, eg. Week 1, week 3, and week 5.

Open-Label Treatment Period (Group B only)

Patients in Group B (the IV treatment groups) will enter a 48-week open-label treatment period and all patients will receive evinacumab 15 mg/kg IV Q4W.

Follow-Up Period (Groups A and B)

All patients will be followed for 24 weeks after the last dose of study drug.

Patients should maintain their stable background LMT regimen from screening through the end of study (EOS) visit.

Patients will be reminded to adhere to a heart-healthy diet at screening, and continuing through the EOS visit. Patients should maintain a stable exercise level for the duration of the study, and avoid rigorous exercise 24 hours before each study visit. All lipid results will be blinded from after randomization until the week 36 visit for the IV cohorts, and until database lock for the SC cohorts.

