8.2.3.3. Electrocardiogram

A standard 12-lead electrocardiogram (ECG) will be performed at time points according to in [Table 1](#), [Table 2](#), [Table 3](#), [Table 4](#), [Table 5](#), [Table 6](#), and [Table 7](#). Electrocardiograms should be performed before blood is drawn during visits that require blood draws.

The 12-lead ECGs should be performed in the supine position after resting for at least 10 minutes. For each ECG recording throughout the study, the electrodes should be positioned at the same place as much as possible. The ECG will be interpreted locally by the investigator. Any new and/or clinically significant changes in ECG parameters should be immediately rechecked for confirmation before making any decision for the concerned patient.

Any clinically significant abnormality should be documented as an AE/SAE, as applicable. Each ECG tracing will be analyzed in comparison with the screening recorded trace. All ECG tracings will be kept as source data (see Section [9.4.5](#)).

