5.8.5. Analysis of 12-Lead ECG

The following definitions will be applied to ECG parameters:

- **Double-blind treatment period:** The treatment period used for quantitative analysis in the double-blind period is defined as the day after the first study drug administration to the day of the last double-blind study drug injection + 7 days for Group A. For Group B, the treatment period is defined from the day after the first administration of double-blind study treatment to the day of the last administration of double-blind study treatment + 28 days for those patients not proceeding into the open-label treatment period, or up to the day of the first open-label study treatment administration for those patients proceeding into the open-label treatment period.
- **Open-label treatment period:** The treatment period used for quantitative analysis in the open-label study period is defined from the day after the first dose of open-label study treatment to the day of the last dose of open label study treatment + 28 days.

For respective treatment period (DBTP and OLTP), ECG parameters will be described through an overall interpretation of ECG status (e.g. normal, abnormal [clinically significant (Yes/No)]). The count and percentage of patients with at least 1 abnormal post-baseline ECG during the respective TEAE period will be summarized according to the following baseline status categories:

- Normal/missing;
- Abnormal

Individual patient ECG measurements will be additionally evaluated by PCSV criteria, specifically identifying patients with at least one post-baseline measurement that meets the PCSV criteria within the TEAE period. The incidence of PCSVs at any time during the respective TEAE periods will be summarized regardless of the baseline level, and again according to the following baseline categories:

- Normal (according to PCSV criterion/criteria)/missing
- Abnormal according to PCSV criterion or criteria

Patient listings of ECG measurements that meet PCSV criteria will be provided for the report appendix.

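### Group B has no scheduled on-treatment ECG after week 48, yet SAP 5.8.5 reports open-label ECG incidence over a period that mixes pre-dose, on-treatment and post-treatment tracings

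*Protocol*

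**What the plan says.** Protocol 5.1 states: "Patients in Group B (the IV treatment groups) will enter a 48-week open-label treatment period", on 15 mg/kg every 4 weeks. Protocol 3.2.2 expects the safety data from this period to "provide the most relevant information to characterize the benefit-risk profile of evinacumab over long-term use".

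The schedule in Protocol 8.1 is as follows.

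- Table 4 marks the row "Electrocardiogram ³" at weeks 24 and 48, and the row "Physical Examination" at week 24 only.
- Table 5 (weeks 52 to 72) has no row for either procedure. Its last column is "End of Open-Label Visit 22", week 72.
- Table 7 marks both procedures at the end-of-study visit, week 92.
- SAP 10.7 reproduces the same marks.

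Protocol 8.2.3.3 says: "A standard 12-lead electrocardiogram (ECG) will be performed at time points according to in" Tables 1 to 7, so Table 5 is included. Protocol 8.2.3.2 gives the same list for the physical examination.

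On analysis, SAP 5.8.5 says: "The count and percentage of patients with at least 1 abnormal post-baseline ECG during the respective TEAE period will be summarized". It uses the same period for ECG values that meet the PCSV criteria. SAP 4.8.1 starts the open-label TEAE period on the day of the first open-label dose and ends it 168 days after the last. For patients who continue, the double-blind TEAE period stops the day before that first open-label dose. SAP 5.8.5 also defines treatment periods: double-blind runs up to the day of the first open-label dose, and open-label runs from the following day to last dose plus 28 days.

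**The concern.** The open-label period exists to give long-term safety information on one regimen, but its scheduled on-treatment ECGs stop halfway through. The visit that closes it is the only end-of-treatment visit with no ECG or physical examination: Group A week 16 and Group B week 24 carry both.

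The reporting rule hides this. A reader of an open-label abnormal-ECG percentage would take it to describe 48 weeks on drug. In fact, the scheduled tracings that can enter it are one taken before open-label dosing began, one at mid-period, and one taken 24 weeks after the last infusion. An abnormality first seen at week 24 would be reported under open label and dropped from the double-blind incidence, although it arose under double-blind treatment.

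**Working it through.** **Schedule days.** Study day = 7 × week + 1. Week 72 gives 7 × 72 + 1 = 505 and week 92 gives 7 × 92 + 1 = 645, both matching Figure 1 of Protocol 5.1. Likewise week 24 is day 169, week 48 is day 337, and the last open-label infusion (week 68) is day 477.

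**Order within a visit.** Protocol 8.1.1 places ECGs before blood draws (footnote 3) and blood draws before dosing (footnote 2). The week 24 and week 48 tracings therefore precede that day's infusion.

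**Coverage.**

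- Open-label span: 505 − 169 = 336 days.
- After the week 48 ECG: 505 − 337 = 168 days (days 338 to 505). 168 / 336 = 50%.
- Infusions every 4 weeks from week 24 to week 68: 12. Six (weeks 24 to 44) precede the week 48 ECG. Six (weeks 48 to 68) have no scheduled on-treatment ECG after them.
- ECG gap, week 48 to week 92: 645 − 337 = 308 days.
- Physical examination gap, week 24 to week 92: 645 − 169 = 476 days.

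**Where each tracing is counted**, for a patient dosed on schedule:

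| Tracing | Day | TEAE period (used for incidence) | Treatment period in SAP 5.8.5 |
|---|---|---|---|
| Week 24, pre-dose | 169 | Open-label (double-blind ends on day 168) | Double-blind |
| Week 48, pre-dose | 337 | Open-label | Open-label |
| Week 92, end of study | 645 | Open-label, last day (477 + 168 = 645) | Neither (open-label ends 477 + 28 = 505) |

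The week 24 tracing qualifies as post-baseline because SAP 6.1 sets baseline before the first double-blind dose. The end-of-study visit has a ±7-day window (days 638 to 652), so with a last infusion on day 477, a tracing on days 646 to 652 falls outside the TEAE period. Whether it counts depends on a few days of visit timing.

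**Meaning of end of treatment (EOT).** Patients who stop drug are to have "an unscheduled visit with assessments normally planned at EOT visit" (Protocol 7.4.2). Protocol 8.1.2 gives that visit as week 24 for the IV group and points to Table 4, which includes both procedures. Protocol 5.1.2 has IV patients followed for a further 20 weeks after EOT: 24 + 20 = 44 matches no end-of-study visit, while 72 + 20 = 92 matches Table 7. That implies week 72, which includes neither procedure.

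**Who enters follow-up.** Protocol 3.2.1 and 5.1 say all patients are followed for 24 weeks after the last dose, and 5.1.2 opens the same way. A later sentence in 5.1.2 sends into follow-up only those who do not join the separate open-label study.

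**The case against.** Several points on the other side stand.

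- The documents name no ECG-specific risk. The potential risks in Protocol 3.2.3 are hypersensitivity, immunogenicity and embryofetal toxicity, and no QT or arrhythmia event is among the evinacumab events of special interest in 9.4.3.
- Between weeks 48 and 72, adverse events and vital signs are collected at every visit, chemistry and hematology are repeated at weeks 60 and 72, and suspected cardiovascular events are adjudicated.
- Safety summaries are descriptive, and physical examinations feed only a listing (SAP 5.8.6).
- Unscheduled ECGs can be used (SAP 6.5), and visit windows allow tracings to be told apart by visit.

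A reader might also infer more than the documents support.

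- *Patients who stop drug during open label get no ECG.* Protocol 8.1.2 points the other way for the IV group. The text is inconsistent, so this cannot be asserted.
- *Patients who roll over have no ECG after week 48.* That relies on one sentence of 5.1.2 against 3.2.1 and 5.1, and the documents give no rollover rate.
- *The citation of Table 5 shows that a week 72 ECG was intended.* The list of Tables 1 to 7 is stock wording. Protocol 8.2.5 uses it for ANGPTL3 from PK samples, although Tables 1 and 2 schedule no PK sample.
- *The only open-label tracing should be moved from week 48 to week 72.* That would leave 48 weeks (72 − 24) between on-treatment tracings instead of 24, and would remove week 48 data that may already be available at the first- and second-step analyses.

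These points limit the severity. They do not answer the reporting problem, because SAP 5.8.5 defines suitable treatment periods and then uses the TEAE period for ECG incidence.

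**Conclusion.** The point holds as a reporting problem with a scheduling inconsistency behind it. Half of the open-label period (168 of 336 days) has no scheduled on-treatment ECG, and no physical examination is scheduled for 476 days. The open-label ECG incidence in SAP 5.8.5 pools three scheduled tracings, of which only the week 48 one is on open-label treatment. Up to 108 Group B patients are affected. This is an upper bound, because not all will enter or complete open label.

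The count assumes that the week 24 ECG and first open-label infusion fall on the same day, as scheduled, and that the last infusion is on day 477. If open-label dosing starts after the day of the week 24 ECG, that tracing stays in the double-blind period. Unscheduled tracings could add coverage, but the plan does not require them. The change is worth making because it is cheap. Efficacy and inference are unaffected.

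**What to change.** 1. In SAP 5.8.5, tabulate abnormal-ECG and ECG-PCSV incidence by the treatment periods that section already defines. The pre-dose week 24 tracing then counts as double-blind, and end-of-study tracings appear separately as post-treatment. State beside the open-label table that scheduled on-treatment ECG coverage ends at week 48, unless the schedule changes.
2. Reconcile Protocol Tables 4 and 5 (and SAP 10.7) with Protocol 8.2.3.2 and 8.2.3.3 on whether week 72 is meant to carry the same ECG and physical examination as the other end-of-treatment visits. Resolving this should not remove the week 48 tracing. If a week 72 ECG is scheduled, day 505 is the last day of the open-label treatment period (477 + 28). With the ±3-day visit window a tracing could fall as late as day 508, so the SAP should say how it is classed.
3. Reconcile what EOT means for patients who stop during open label (Protocol 5.1.2, 7.4.2, 8.1.2), and whether patients who join the separate open-label study enter follow-up (3.2.1 and 5.1 against 5.1.2).

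The cost is one extra table split and text edits. If the schedule is aligned, add one ECG and one examination per patient at an existing clinic visit.
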